3.1. Primary Objectives

This is phase 4 academic, prospective, randomized, open-label, interventional study designed to investigate the efficacy of sargramostim (Leukine®) in improving oxygenation and short- and long-term outcome of COVID-19 patients with acute hypoxic respiratory failure. There are currently no treatments directed at improving lung repair and local immunity in COVID-19 patients, and no treatment that attempt to halt the progression from manageable acute hypoxic respiratory failure to ARDS in patients with COVID-19 infection.

Justification for our objective is that preventing progression from early acute hypoxic respiratory failure to ARDS could have a huge impact on the foreseeable overflow of the ICU units, that is already happening in some countries and is bound to happen on a global scale. The outcome of our study could thus have large impact from a medical, ethical and economic perspective.

The **hypothesis of the proposed intervention** is that GM-CSF has profound effects on antiviral immunity, can provide the stimulus to restore immune homeostasis in the lung with acute lung injury post COVID-19, and can promote lung repair mechanisms, that lead to a 25% improvement in lung oxygenation parameters.

This hypothesis is based on experiments performed in mice showing that GM-CSF treatment can prevent mortality and prevent ARDS in mice with post-viral acute lung injury.

To address our hypothesis, we will randomize patients with confirmed COVID-19 with acute hypoxic respiratory failure (saturation below 93% on minimal 2 l/min O₂ or PaO₂/FiO₂ <350) to receive sargramostim 125mcg twice daily for 5 days as a nebulized inhalation on top of standard of care (active group), or to receive standard of care treatment (control group). Upon progression of disease requiring initiation of non-invasive or invasive mechanical ventilatory support within the 5 day period, in patients in the active group, inhaled sargramostim will be replaced by intravenous sargramostim 125mcg/m² body surface area once daily until the 5 day period is reached.

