9.1. Randomization

In this open label trial patients will be randomized in a 1:1 ratio. Randomization in Belgium will be done using REDCap (electronic IVRS system).

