12.1. Sample size calculation

The outcome(s) on which the sample size calculation is based upon, is the primary endpoint measurement of oxygenation, defined as ratio of $\text{PaO}_2/\text{FiO}_2$ and P(A-a)O_2 .

Sample calculation and power analysis have been performed using Genstat. The target difference is the difference measured at the primary endpoint (at day 6) between the control and the treated group. Given a sample size of 40 patients each, a minimal improvement of 10% in the treated group relative to the control group will be detected as significant at a significance level of 0,01 with a power of 0.90. The error variance was set at 100 units, corresponding with a standard deviation of 10 units.

The post-treatment evaluations should be assessed within 24 hours of the last dose of treatment. That is, Day 6 will be the timepoint for measures of efficacy endpoints based on 5 days of treatment, and Day 10 for patients who complete 10 days of treatment. If the patient is discharged from hospital prior to the day 6 (or day 10) efficacy evaluations, the values at day of discharge will be used as value for measuring efficacy endpoints.

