Comparison will be between active group A receiving sargramostim on top of standard of care and control group B receiving standard of care. The change from baseline and daily change from baseline in oxygenation/respiratory parameter of P(A-a)O_2 gradient, ratio of $\text{PaO}_2/\text{FiO}_2$ and ratio of $\text{SpO}_2/\text{FiO}_2$ will be evaluated and summarized between group A and group B at Day 6. The difference of change from baseline between two groups will be tested by a t-test. In general, the last observed measurement prior to the first dose of study treatment occurred on Day 1 visit will be considered the baseline measurement. Day 6 is the primary analysis point. If the patient leaves hospital prior to the day 6 analysis point, oxygenation at day of discharge will be used as value for measuring primary endpoint.

The analyses described above will also be performed between group A (early 5 day intervention with sargramostim) and group D (late 5 day intervention with sargramostim). Change from baseline (D1) to Day 10, daily change from baseline (D1) at Day 10 in oxygenation/respiratory parameter of P(A-a)O_2

gradient, ratio of $\text{PaO}_2/\text{FiO}_2$ and ratio of $\text{SpO}_2/\text{FiO}_2$ will be summarized as well. A t-test will be conducted to compare the difference between the groups.

The same analyses will be repeated for pathological oxygenation parameter of P(A-a)O_2 gradient, ratio of $\text{PaO}_2/\text{FiO}_2$ and ratio of $\text{SpO}_2/\text{FiO}_2$ including summary of their value and change from baseline at Day 6 and Day 10. A waterfall plot will be used to represent the change from baseline and percentage change from baseline on Day 6 for 1) oxygenation parameter of P(A-a)O_2 gradient; 2) pathological oxygenation parameter of P(A-a)O_2 gradient; 3) ratio of $\text{PaO}_2/\text{FiO}_2$; 4) ratio of $\text{SpO}_2/\text{FiO}_2$. Percentage change from baseline of P(A-a)O_2 gradient and ratio of $\text{PaO}_2/\text{FiO}_2$ on Day 6 and follow-up will be summarized.

Reasons of missing AA gradient values on Day 6 will also be summarized.

The normal value of AA gradient for room air is calculated as: $2.5 + (0.21 \times \text{Age})$. All the results including change from baseline, and maximum change from baseline after 5 day intervention with sargramostim, normal AA gradient value for room air and flag of abnormality on Day 6 will be listed.

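### The stated 90% power for a 10% improvement does not follow from the inputs in section 12.1, and its single SD of 10 units is implausibly small, above all for PaO2/FiO2

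*Protocol*

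**What the plan says.** Protocol section 12.1 bases the sample size on the primary oxygenation endpoint, which it defines as both PaO2/FiO2 and P(A-a)O2. On the effect it says: "The target difference is the difference measured at the primary endpoint (at day 6) between the control and the treated group". The remaining inputs are:

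- Sample size: "Given a sample size of 40 patients each". Section 9.1 adds that "patients will be randomized in a 1:1 ratio".
- Effect: "a minimal improvement of 10% in the treated group relative to the control group will be detected as significant".
- Error rates: "at a significance level of 0,01 with a power of 0.90".
- Spread: "The error variance was set at 100 units, corresponding with a standard deviation of 10 units".

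Section 12.1 names no unit, control mean, source for the SD, sidedness or allowance for loss. It does not say whether the SD describes the Day 6 value or the change from baseline. For the continuous comparison, section 12.2 states: "The difference of change from baseline between two groups will be tested by a t-test". Section 3.1 hypothesises that treatment effects will "lead to a 25% improvement in lung oxygenation parameters".

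**The concern.** The effect is a percentage and the SD is in unnamed units. The two can be combined only through a control mean, and none is given. One SD is also used for two quantities with different scales.

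The size of the SD is a second problem. Patients may enter with PaO2/FiO2 up to 350, so that measure runs in the hundreds, and an SD of 10 would mean that patients hardly differ from one another.

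This paragraph is the only justification the protocol gives for 80 patients. If the 90% figure is taken at face value, a null result could be read as ruling out a 10% effect when the trial may have had little chance of finding one.

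**Working it through.** **Inputs from the protocol.** n = 40 per arm, alpha = 0.01, SD = 10 units, effect 10% (section 12.1); two-sample t-test (section 12.2); PaO2/FiO2 entry limit 350 (section 6.1); FiO2 table (section 9.2); gradient formula (section 12.2). **Assumed here:** two-sided testing, and atmospheric minus water-vapour pressure of 760 − 47 = 713 mmHg.

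**1. Trying to reproduce 0.90.** For a standardised difference d = difference/SD, the noncentrality is d × √(n/2) = d × √20. By the noncentral t on 78 degrees of freedom:

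- 90% power at two-sided 0.01 needs d = 0.881, which is 8.8 units at SD 10. The normal approximation, (2.576 + 1.282) × √(2/40) = 0.863, gives 8.6 units.
- If 10% means 10 units, d = 1 and power is 0.964 (normal approximation 0.971). Only 32 per arm would be needed for 90%.
- One-sided, 10 units has power 0.981, further from 0.90.

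**2. What would bring 0.90 back.**

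- A control mean of 8.8/0.10 = 88 units.
- An SD of 10/0.881 = 11.3 with a 10-unit effect.
- 20% loss, leaving 40 × 0.8 = 32 evaluable per arm, with a 10-unit effect: power 0.906.

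The text states none of these.

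**3. Is an SD of 10 credible for PaO2/FiO2?** On room air, 10 units is 10 × 0.21 = 2.1 mmHg of PaO2. On supplemental oxygen, FiO2 is read from a table of flow bands. Holding PaO2 fixed, a move from 28% to 32% changes the ratio by:

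- PaO2 60: 60/0.28 − 60/0.32 = 26.8 units.
- PaO2 80: 80/0.28 − 80/0.32 = 35.7 units.

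At PaO2 70, all five nasal steps exceed 10 units, as do 25 of the 28 steps over all devices.

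**4. The same question for the gradient.** A step in FiO2 changes the gradient by step × 713, other terms fixed. A 4-point step gives 0.04 × 713 = 28.5 mmHg. The smallest step in the table, 2 points, gives 0.02 × 713 = 14.3 mmHg. Every step therefore exceeds 10 units.

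**5. Power if the SD is larger.** Illustration for PaO2/FiO2 with an assumed control mean of 250, so that 10% is 25 units and 25% is 62.5 units; 40 per arm, two-sided 0.01:

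| Assumed SD | Power for 10% | Power for 25% |
|---|---|---|
| 50 | 0.349 | 0.998 |
| 75 | 0.132 | 0.858 |
| 100 | 0.069 | 0.563 |

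For 90% power to detect 25 units, the SD must be no more than 25/0.881 = 28.4.

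**The case against.** The strongest reply is that section 12.1 is incomplete and contains no calculation error. A control mean of 88 is an ordinary value for the gradient: with assumed values FiO2 0.28, PaO2 68 and PaCO2 35, the section 12.2 formula gives 0.28 × 713 − 35/0.8 − 68 = 87.9 mmHg, and 10% of that is the 8.8 units that have 90% power. An unstated 20% loss would also explain the figure. This stands as a possible explanation. It does not make the figure follow from what is written, and it does not help PaO2/FiO2, for which a mean near 88 is out of scale with an entry limit of 350.

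A reader might infer that the FiO2 table makes an SD of 10 impossible. The protocol does not support that. Sections 4.1 and 9.2 prefer measurement on room air, where no table step arises, and the documents do not say how many patients will need oxygen. A step at fixed PaO2 is not an SD. A few PaO2/FiO2 steps are also below 10 units: at PaO2 70, face mask 38% to 40% is 9.2, and reservoir mask 80% to 90% and 90% to 95% are 9.7 and 4.1. For the gradient on room air alone, an SD of 10 is less clearly excluded.

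A reader might also infer that the trial is shown to be too small. It is not. On the 10-unit reading, 0.90 understates the power. The doubt about power rests on the SD, and the SDs of 50 to 100 used above are assumptions.

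Nor does a 25% hypothesis contradict a 10% detectable difference. The 25% in section 3.1 has no stated comparator, and planning to detect less than the hypothesised effect is conservative.

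**Conclusion.** The point holds in this form: the power stated in section 12.1 is not supported by its own inputs, and the SD of 10 is implausibly small for PaO2/FiO2 and doubtful for the gradient in patients on oxygen. What the inputs do support is 90% power for 0.88 SD at two-sided 0.01, whatever the measure.

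The true power for a 10% difference is unknown. For PaO2/FiO2 it is probably well below 0.90, and it would reach 0.90 only with an SD of about 28 or less at a control mean of 250. The 35%, 13% and 7% figures depend on that assumed mean and on assumed SDs, which would have to apply to the change from baseline that is tested. Under the same assumptions, power for a 25% between-group difference is 99.8%, 86% and 56%, so 80 patients may be defensible for an effect of that size. Section 12.1 does not make that case.

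**What to change.** Keep 80 patients and rewrite the power paragraph of section 12.1:

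- State that 40 per arm gives 90% power at two-sided 0.01 for a difference of 0.88 SD.
- For each primary measure, in its own units and for the quantity tested (change from baseline to Day 6), give the control mean on which the percentage is based and an SD with its source, or a stated range of SDs.
- Give the resulting power for 10% and for the hypothesised 25%.
- State any allowance for loss that the calculation used.
- Remove the unconditional claim of 90% power for 10% unless these inputs support it.

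The cost is one paragraph. No patients are added and no endpoint or test changes. The stated power may become less favourable.

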4.2. Secondary End Points + Time Points

- to study if early intervention with sargramostim is safe (number of AEs/SAEs)

Although sargramostim has been given previously by inhalation to patients with ARDS and interstitial lung disease, data on safety in patients with COVID-19 infection are currently lacking. Since we are randomizing against 5 days of no sargramostim treatment, comparison of AEs and SAEs between group A and group B will be very informative.

-to study if early intervention with inhaled sargramostim affects clinical outcome defined by Length of hospital stay

Mean and median change in 6-point ordinal scale change between day 1, day 6

Mean and median change in clinical sign score between day 1 and day 6

Time to clinical sign score <6 maintained for 24h

Mean and median change of SOFA score between day 1 and day 6 or between day 1 and day 10.

Mean and median change NEWS2 score between day 1 and day 6 or between day 1 and day 10.

Time to NEWS2 score less than 2 for at least 24h

- to study if early intervention with sargramostim affects the rate of nosocomial infection

Patients with viral respiratory infection are at risk of secondary bacterial infections. As part of routine clinical care, sputum samples will be collected in patients suspected of secondary bacterial pneumonia, and checked for the presence of bacteria.

-to study if early intervention with inhaled sargramostim affects progression to mechanical ventilation and/or ARDS

Decreasing oxygenation often leads to the need for non-invasive or invasive mechanical ventilation, and if severe enough to a diagnosis of ARDS. We will therefore as a secondary endpoint also study if early intervention with inhaled sargramostim prevents progression to criteria-defined ARDS (according to the American-European Consensus Conference (AECC) diagnostic criteria for ARDS: acute onset; ratio of partial pressure of arterial oxygen to fraction of inspired oxygen (PaO_2/FiO_2) of 200 or less, regardless of positive end-expiratory pressure; bilateral infiltrates seen on frontal chest radiograph; and pulmonary artery wedge pressure of 18 mm Hg or less when measured, or no clinical evidence of left atrial hypertension), requiring high-flow oxygen devices, non-invasive mechanical ventilation, mechanical ventilation, by measuring the day from admission when this diagnosis is made or therapies are initiated.

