On days 1-5, patients in group A will inhale sargramostim 125mcg twice daily for 5 days as a nebulized inhalation using a Philips InnoSpire Go portable mesh nebulizer on top of standard of care. This device is a handheld mesh nebulizer that can be fitted with a facial mask. Patients will be instructed prior to receiving the first dose on how to use this simple device, by a physician. This procedure is finished in 5-10 minutes, and will be performed twice daily, in the morning (between 6 a.m. and 11 a.m.) and evening (between 6 p.m. and 11 p.m.).

Upon progression of disease requiring initiation of non-invasive or invasive mechanical ventilatory support within the 5 day period, in patients in the active group, inhaled sargramostim will be replaced by intravenous sargramostim 125mcg/m² body surface area once daily until the 5 day period is reached. This administration will occur via a centrally placed catheter or peripheral catheter, that will be in place as part of routine medical care at the ICU.

On a final clinical visit between week 10-20 an additional serum tube (5ml) and an EDTA tube (10 ml) will be taken in selected centers.

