^a Patients randomized in the treatment group will receive inhaled sargramostim from D1 until D5. In case of progression requiring mechanical ventilation within the first 5 days, IV sargramostim can be initiated until the 5 day period is reached. From day 6 onwards, progressive patients in the active group will have the option to receive an additional 5 days of IV sargramostim, based on the treating physician’s assessment. Patients in the control group will have the option to receive 5 days of IV sargramostim in case of progression requiring mechanical ventilation, based on the treating physician’s assessment. IMP should always be administered after other assessments, where possible.

^o 6 MWT: to assess the distance walked over 6 minutes as submaximal test of aerobic capacity/endurance.

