12.2. Type of statistical methods

All endpoints will be summarized and where relevant represented graphically

A detailed statistical analysis plan (SAP) has been set up by EffectStats LLC, Cambridge Massachusetts, USA. The statistical tests to be used to look at improvements in oxygenation between treatment groups will be a Chi-square test. Mortality frequencies will be analyzed using Wald test.

Key timepoints of interest for endpoints include Day 6 and Day 11, where data are available. All available efficacy data will be tabulated and presented for all patients in the mITT Population.

Oxygenation after 5 days of Sargramostim Intervention

To measure the effectiveness of sargramostim on restoring lung homeostasis, the primary endpoint of this intervention is measuring oxygenation after 5 days of inhaled (and intravenous) treatment through assessment of pretreatment and post-treatment ratio of $\text{PaO}_2/\text{FiO}_2$, $\text{SpO}_2/\text{FiO}_2$ and through measurement of the P(A-a)O_2 gradient. During the 5 day treatment period, daily measurements of oxygen saturation (pulse oximetry) in relation to FiO_2 will be performed. Negative value of P(A-a)O_2 gradient would be removed from the primary analysis.

P(A-a)O_2 gradient, $\text{PaO}_2/\text{FiO}_2$ ratio and $\text{SpO}_2/\text{FiO}_2$ are defined as:

$\text{P(A-a)O}_2 \text{ gradient} = [(\text{FiO}_2) \times (\text{Atmospheric Pressure} - \text{H}_2\text{O Pressure}) - (\text{PaCO}_2/0.8)] - \text{PaO}_2$

$\text{PaO}_2/\text{FiO}_2 = \text{Partial Pressure Oxygen/Fraction of Inspired Oxygen} \times 100$

$\text{SpO}_2/\text{FiO}_2 = \text{Oxygen Saturation/ Fraction of Inspired Oxygen} \times 100$

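### The Day 10 evaluation set for patients treated for 10 days normally falls before their last IV dose, and the protocol names Day 11 elsewhere

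*Protocol*

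**What the plan says.** Section 12.1 states the timing rule: "The post-treatment evaluations should be assessed within 24 hours of the last dose of treatment". It then applies the rule twice. For the first course, "Day 6 will be the timepoint for measures of efficacy endpoints based on 5 days of treatment"; for the longer course, "and Day 10 for patients who complete 10 days of treatment". Discharge values stand in if the patient leaves earlier.

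The dosing calendar is in sections 9.2 and 9.4. For the first course, "On days 1-5, patients in group A will inhale sargramostim 125mcg twice daily for 5 days". For the extension, "From day 6 onwards, progressive patients in the active group will have the option to receive an additional 5 days of IV sargramostim". Section 1.6 gives the control arm the option of a five-day, once-daily IV course, also from day 6. No section gives a latest start day. On the order of events within a day, the flowchart footnote says "IMP should always be administered after other assessments, where possible".

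The later time point is named in two ways. Section 12.2 opens with "Key timepoints of interest for endpoints include Day 6 and Day 11, where data are available", but further on it analyses change from baseline to Day 10 and applies a t-test, including to group A against group D. Sections 3.2 and 4.2 also use Day 10, for example "Mean and median change of SOFA score between day 1 and day 6 or between day 1 and day 10". The flowchart in section 9.4 has columns for D7-D9 and D10 and then goes straight to follow-up.

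**The concern.** One rule should give one kind of answer. Day 6 is the day after the last dose of the first course, whereas Day 10 is at best the day of the last dose of a ten-day course. A site that follows the flowchart and its footnote would usually record the Day 10 values before that day's infusion. The analysis would then label as post-treatment a value taken while the course was still running.

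Two analyses are touched. The first is the Day 10 post-treatment summary for active-arm patients who go on to the extension (group C). The second is the Day 10 t-test of group A against group D in section 12.2. There, group A without extension finished dosing on day 5, while group D is in mid-course or may not have started. How much IV treatment a patient has had by Day 10 depends on the start day, which the protocol leaves open.

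The conflict between Day 10 and Day 11 is a separate practical problem: an analyst who takes Day 11 from section 12.2 finds no scheduled visit to supply the data.

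**Working it through.** **Inputs.** First course: days 1 to 5 (section 9.2). IV course: five once-daily doses, starting on day 6 or later (sections 1.6, 7.1.1 and 9.4). Assessment before dose on the same day, where possible (section 9.4). Evaluation within 24 hours of the last dose (section 12.1).

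**Step 1: reproduce Day 6.** Last dosing day = 1 + 5 − 1 = 5. The next day is 6. The plan's figure is reproduced.

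**Step 2: apply the same convention to ten days.** With no gap, the extension starts on day 6 and its last dose is on day 6 + 5 − 1 = 10. The next day is 11. The plan's Day 10 is not reproduced; section 12.2's Day 11 is.

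**Step 3: let the start day vary.** If IV dosing starts on day s (s ≥ 6), then:

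- last dose: day s + 4
- day after the last dose: s + 5
- doses received before a pre-dose Day 10 assessment: 10 − s, not below 0
- doses received if Day 10 is assessed after that day's infusion: 11 − s, not below 0

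| IV start day | Last dose | Day after last dose | IV doses by Day 10, assessed pre-dose | IV doses by Day 10, assessed post-dose |
|---|---|---|---|---|
| 6 | 10 | 11 | 4 of 5 | 5 of 5 |
| 7 | 11 | 12 | 3 | 4 |
| 8 | 12 | 13 | 2 | 3 |
| 9 | 13 | 14 | 1 | 2 |
| 10 | 14 | 15 | 0 | 1 |
| 11 | 15 | 16 | 0 | 0 |

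Only one cell shows a complete course: a day 6 start with the assessment made after the day 10 infusion.

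**Step 4: how many patients.** Section 7.1.1 expects some 30% of each arm of 40 to deteriorate: 0.30 × 40 = 12 per arm. IV treatment is at the physician's option, so 12 in group C and 12 in group D are upper figures under that estimate. The protocol gives no distribution of start days.

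**Step 5: compare the sections.** Day 10 stands in 3.2, 4.2, 12.1, the later part of 12.2 and the flowchart. Day 11 stands in the opening of 12.2 only. These are all current text.

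**The case against.** The best defence is that the gap is one day and the label can bear it. The dosing order in section 9.4 applies only where possible. A day 6 starter assessed after the day 10 infusion has had all five doses and satisfies the 24-hour rule. That is correct, so a reader should not infer that no patient can have completed the course by Day 10. But it rescues only day 6 starters assessed against the stated order.

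Other stronger readings are tempting and are not supported:

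- **That group D breaches the 24-hour rule.** The Day 10 sentence in section 12.1 covers patients who complete 10 days of treatment, and group D receives five. Day 10 reaches group D only through section 12.2, where it is a calendar-time change from day 1.
- **That Day 10 SOFA and NEWS2 are presented as results of the IV course.** Sections 3.2 and 4.2 list them under the early inhaled intervention, which is the randomised question.
- **That the IV course is made to look worse.** Late starters would be measured close to their deterioration, so this is plausible, but nothing in the document establishes a direction or size.
- **That patients will be evaluated with no IV dose at all.** This requires a start on day 10 or later. The protocol sets no limit against it, but the flowchart shows study drug only up to D10 and section 1.7 gives 10 days of total treatment. If dosing did end on day 10, anyone starting after day 6 could not receive the stated five days, so these passages need reconciling in any case.

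A statistical analysis plan that is not shown here might define visit windows. It would not remove a contradiction that stands in the protocol itself.

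**Conclusion.** The point holds in limited form. Under the protocol's own 24-hour rule, the convention that gives Day 6 for the first course gives Day 11 for an uninterrupted ten-day course. Under the stated order of assessment and dosing, the Day 10 value follows at most 4 of 5 IV doses, falling by one for each day that the start is delayed. Section 12.2 contradicts section 12.1 on the day, and the flowchart cannot supply Day 11.

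The consequence is confined to the Day 10 post-treatment summaries in extended patients and the Day 10 comparison of A with D. The Day 6 primary endpoint, its A-versus-B comparison and the sample size are untouched. The day count assumes once-daily dosing without interruption; the counts for late starts assume that no latest start day applies, since none is stated.

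A corrected evaluation day would not make A against D a fair comparison. Group D is selected on progression after randomisation, and section 7.1.1 describes group A as patients without deterioration after five days.

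**What to change.** Reconcile sections 9.4 (flowchart and study-drug footnote), 12.1 and 12.2 on one post-course evaluation: the day after the last IV dose actually received, or discharge if earlier. For an uninterrupted course on days 1 to 10 this is Day 11. Add the visit to the flowchart and remove the competing Day 10 and Day 11 labels.

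Keep Day 10 SOFA, NEWS2 and oxygenation as calendar-time comparisons by randomised arm, not called post-treatment. Describe the comparison of A with D as descriptive.

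The cost is a wording change and one flowchart column, for up to about 24 inpatients on the protocol's estimate. There are three drawbacks:

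- The post-course assessment will fall on different calendar days.
- Patients who die before it will have no value and should be counted in the summary.
- Arterial blood gas is scheduled at D1, D6 or discharge, and follow-up, so at neither Day 10 nor Day 11. Post-course oxygenation would rest on SpO2/FiO2 or on gases taken for clinical reasons, unless a sample is added.

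None of this implies a change to dosing.
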